NOTE: Protocol specific exceptions to expedited reporting of serious adverse events are found in section 10.41 of the protocol.

Expedited AE reporting timelines are defined as:

- “24-Hour; 3 Calendar Days” - The AE must initially be reported via MedWatch within 24 hours of learning of the AE, followed by a complete expedited report within 3 calendar days of the initial 24-hour report.
- “7 Calendar Days” - A complete expedited report on the AE must be submitted within 7 calendar days of learning of the AE.

¹Serious adverse events that occur more than 30 days after the last administration of investigational agent/intervention and have an attribution of possible, probable, or definite require reporting as follows:

Expedited 24-hour notification followed by complete report within 3 calendar days for:

- All Grade 4, and Grade 5 AEs

Expedited 7 calendar day reports for:

- Grade 2 adverse events resulting in hospitalization or prolongation of hospitalization
- Grade 3 adverse events

² For studies using PET or SPECT IND agents, the AE reporting period is limited to 10 radioactive half-lives, rounded UP to the nearest whole day, after the agent/intervention was last administered. Footnote “1” above applies after this reporting period.

Effective Date: May 5, 2011

Additional Instructions:

1. An increased incidence of an expected adverse event (AE) is based on the patients treated for this study at their site. A list of known/expected AEs is reported in the package insert or the literature, including AEs resulting from a drug overdose.
2. Submit form to the FDA, [REDACTED]
[REDACTED]
[REDACTED]
[REDACTED]

Reporting Serious Adverse Events to Acrotech Biopharma: The Investigator must notify Acrotech Biopharma of any event that meets one of the criteria for an SAE within 24 hours of first knowledge. For the initial report, please complete a standard MedWatch form and email to [REDACTED] with all relevant documentation (laboratory tests, hospital admission/discharge summary, etc.). Please assure that patient identifiers are redacted from all documentation, except for patient initials and date of birth.

Acrotech Biopharma:

SAE Email: [REDACTED]

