10.41 Special Situations for Expedited Reporting

EXPECTED Serious Adverse Events

An expedited report may not be required for specific Grade 1, 2, 3 and 4 Serious Adverse Events where the AE is **EXPECTED**. Any protocol specific reporting procedures MUST BE SPECIFIED BELOW and will supercede the standard Expedited Adverse Event Reporting Requirements. Note: These adverse events must still be reported through the routine reporting mechanism [i.e. Nadir/Adverse Events Form]; see footnote 1.

System Organ Class (SOC)	Adverse event/ Symptoms	CTCAE Grade at which the event will not be expeditedly reported. ¹
Blood and lymphatic system disorders	Anemia	≤ Grade 4
Investigations	White blood cell decreased	≤ Grade 4
	Lymphocyte count decreased	≤ Grade 4
	Neutrophil count decreased	≤ Grade 4
	Platelet count decreased	≤ Grade 4

¹ These exceptions only apply if the adverse event does not result in hospitalization. If the adverse event results in hospitalization, then the standard expedited adverse events reporting requirements must be followed.

Specific protocol exceptions to expedited reporting should be reported expeditiously by investigators **ONLY** if they exceed the expected grade of the event.

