10.6 Required Routine Reporting

Adverse events to be graded at each evaluation and pretreatment symptoms/conditions to be evaluated at baseline per the CTCAE v4.0 grading unless otherwise stated in the table below:

System Organ Class (SOC)	Adverse event/Symptoms	Baseline	Each evaluation
Investigations	Neutrophil count decreased	X	X
	Platelet count decreased	X	X
	White blood cell decreased	X	X
Skin and subcutaneous tissue disorders	Rash maculo-papular	X	X

10.61 Submit via appropriate MCCC Case Report Forms (i.e., paper or electronic, as applicable) the following AEs experienced by a patient and not specified in Section 10.6

10.611 Grade 2 AEs deemed *possibly, probably, or definitely* related to the study treatment or procedure.

10.612 Grade 3 and 4 AEs regardless of attribution to the study treatment or procedure.

10.613 Grade 5 AEs (Deaths)

10.6131 Any death within 30 days of the patient's last study treatment or procedure regardless of attribution to the study treatment or procedure.

10.6132 Any death more than 30 days after the patient's last study treatment or procedure that is felt to be at least possibly treatment related must also be submitted as a Grade 5 AE, with a CTCAE type and attribution assigned.

10.62 Refer to the instructions in the Forms Packet (or electronic data entry screens, as applicable) regarding the submission of late occurring AEs following completion of the Active Monitoring Phase (i.e., compliance with Test Schedule in Section 4.0).

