16.34 Adverse Events: All eligible patients that have initiated treatment will be considered evaluable for assessing adverse event rate(s). The maximum grade for each type of adverse event will be recorded for each patient, and frequency tables

will be reviewed to determine patterns. Additionally, the relationship of the adverse event(s) to the study treatment will be taken into consideration. Rates of individual adverse events (grade 3 and higher) will be compared between arms using a Fisher's exact test.

16.4 Correlative Research: The correlative endpoints listed below will be evaluated in each arm independently and may also be compared between the two arms. For each measure, values may be investigated with respect to response (CR vs. less than CR) using two-sample t-tests (continuous measures) or chi-square tests (categorical measures). Relationship with time to event measures (PFS, TTNT, TTC) will be evaluated using Kaplan-Meier methods and log-rank statistics (categorical measures) or Cox proportional hazards models (continuous measures). For values collected at more than one time point, changes over time will be evaluated using paired-t-tests (continuous measures) or McNemar's or Bhapkar's tests (categorical measures). Endpoints and additional analyses are described below. Analysis involving quality of life are described in Section 16.47.

- 16.41 The incidence of exon 2 bcl2 mutations will evaluated at baseline.
- 16.42 Tissue Tregs and tissue monocytes will be quantified for the on study tumor biopsies. These values will be reported as percentages.
- 16.43 Serum cytokines will be analyzed for each time point (pre-treatment and 6 months). Each cytokine will be evaluated in reference to normal controls and levels will be categorized as normal, elevated, or suppressed.
- 16.44 Vitamin D levels will be evaluated at on study. At each time point, Vitamin D level will be categorized as normal (sufficient) vs. abnormal (insufficient). Vitamin D insufficiency will be defined as a 25 hydroxy-vitamin D (D2 + D3) level <25 ng/mL in the central (Mayo) laboratory.

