18.0 Records and Data Collection Procedures

18.1 Submission Timetable

Initial Material(s)

Case Report Form (CRF)	Active-Monitoring Phase (Compliance with Test Schedule Section 4.0)
On-Study	≤14 days after registration
Adverse Event– Baseline	
Measurement – Baseline	
Tumor Tissue Biopsy Pathology Report	
CT/PET/MRI Scan Report	
Research Paraffin Embedded Submission – Baseline (All Patients)	≤30 days after registration
Research Fresh Tissue Submission – Baseline (Mayo Patients only)	
Research Blood Submission	≤ 21 days after registration
End of Active Treatment/Cancel Notification	Submit ≤14 days after registration if withdrawal/refusal occurs prior to beginning protocol therapy
Patient Questionnaire Booklet	≤14 days after registration - Patient questionnaire booklet must be used; copies are not acceptable for this submission.
Booklet Compliance	≤14 days after registration - This form must be completed only if the patient questionnaire booklet contains absolutely NO patient provided assessment information.

Central Pathology Review Material(s)

CRF	Active-Monitoring Phase (Compliance with Test Schedule Section 4.0)
Pathology Materials (this is for central review, eligibility, etc.)	Submit ≤30 days after registration (see Section 17.0)

Test Schedule Material(s)

CRF	Active-Monitoring Phase (Compliance with Test Schedule Section 4.0)		
	At each evaluation during treatment	At end of treatment	Observation
Evaluation/Treatment	X ²	X	

CRF	Active-Monitoring Phase (Compliance with Test Schedule Section 4.0)		
	At each evaluation during treatment	At end of treatment	Observation
Evaluation/Observation			X ¹
Nadir/Adverse Event (Cycles 1 & 2 Only)	X	X	X ³
Measurement	X	X	X
Research Blood Submission			X (see Section 14.0)
Patient Questionnaire Booklet ⁴	X	X	X
Booklet Compliance ⁵	X	X	X
End of Active Treatment/Cancel Notification		X	
ADR/AER	At each occurrence (see Section 10.0)		At each occurrence (see Section 10.0) ³
CT/PET/MRI Scan Report	X ⁶		X ⁶

1. Complete at each evaluation during Observation (see Section 4.0).
2. Complete at each evaluation during Active Treatment (see Section 4.0).
3. AE form and expedited reports needed for Cycle 1 (treatment – months 0-3) and Cycle 2 (first cycle of observation – months 3-6) only.
4. Patient questionnaire booklet **must** be used; copies are not acceptable for this submission.

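### The submission timetable ends expedited adverse event reports at month 6, while Section 10.4 requires late attributable serious events to be reported with no end date

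*Combined protocol and SAP*

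**What the plan says.** The Section 18.1 timetable for active monitoring has two rows for adverse events. The routine form is labelled "Nadir/Adverse Event (Cycles 1 & 2 Only"), and its observation-phase entry carries footnote 3. The ADR/AER row reads "At each occurrence (see Section 10.0") for both the treatment and observation phases, and footnote 3 is attached to the observation entry. That footnote says "AE form and expedited reports needed for Cycle 1" and Cycle 2, and closes with the word only; it defines these cycles as months 0-3 and 3-6.

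Section 10.4, footnote 1, covers serious "adverse events that occur more than 30 days after the last administration of investigational agent/intervention" that are possibly, probably or definitely attributed to treatment. Grades 4 and 5 need notification within 24 hours and a full report within 3 calendar days. Grade 3 events, and grade 2 events with hospitalization, need a report within 7 calendar days. No closing date is given.

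Section 10.41 exempts expected cytopenias up to grade 4 from expedited reporting if the patient is not hospitalized, and adds: "These adverse events must still be reported through the routine reporting mechanism [i.e. Nadir/Adverse Events Form"]. Section 15.27 warns that cytopenia after Zevalin can be delayed and prolonged. Section 4.0 marks adverse event assessment at baseline, month 3 and month 6, but blood counts through month 60.

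For the analysis, Section 16.34 states "The maximum grade for each type of adverse event will be recorded for each patient". It also reviews frequency tables, considers attribution, and compares rates of grade 3 or higher between arms.

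**The concern.** Two instructions in one protocol give opposite answers to a practical question: after month 6, does a site file an expedited report for a serious event that may be due to treatment? Section 10.4 says yes and the timetable footnote says no. The timetable is the page that data staff work from, so the conflict could lead to under-reporting.

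Patients are candidates for observation (Section 3.14), so late harm matters when weighing a gain in complete response. A hospitalized cytopenia at month 9 in a Zevalin patient is the kind of event that Section 15.27 anticipates and that footnote 3 would let a site leave out. Section 16.3 repeats the secondary analyses, which include adverse events, at 3 and 5 years. If reports stop at month 6, those later tables may add little or nothing on adverse events.

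**Working it through.** No figure in the plan needs reproducing. The check sets the texts side by side, counts the time affected, and works one case through.

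**1. What footnote 3 changes.** The routine form's row label already limits it to Cycles 1 and 2, so the footnote adds nothing there. Its separate effect falls on the ADR/AER observation cell. The footnote names expedited reports explicitly, so this cannot be put down to a misplaced superscript.

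**2. When the rules diverge.** The last dose is on day 22 in Arm A (Section 7.1) and day 8 in Arm B (Section 7.2). Section 10.4, footnote 1, therefore applies after day 22 + 30 = 52 in Arm A and day 8 + 30 = 38 in Arm B. From then to month 6 both texts call for a report. After month 6 they disagree:

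| Period | 18.1, footnote 3 | 10.4, footnote 1 |
|---|---|---|
| 30 days after last dose to month 6 | report | report if attributable |
| Month 6 to month 60 | not needed | report if attributable |

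The span in conflict is 60 - 6 = 54 months, and 54/60 = 90% of active monitoring. Of the 10 post-treatment visits, 2 (months 3 and 6) fall inside the window and 8 (months 9, 12, 18, 24, 30, 36, 48 and 60) fall outside.

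**3. A worked case.** An Arm B patient still in observation is hospitalized for more than 24 hours at month 9 with grade 3 neutropenia, possibly related. The Section 10.41 exemption is lost because of the hospitalization. Section 10.4, footnote 1, asks for a complete report within 7 calendar days. Section 18.1, footnote 3, asks for none.

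**4. Whether another section settles it.**
- Section 10.52 (attributable deaths) and Section 10.53 (secondary malignancy) set no month-6 limit. Both are worded for agents under an IND/IDE, whereas the Section 10.4 table is headed for commercial agents in a non-IND/IDE trial.
- Section 10.612 requires "Grade 3 and 4 AEs regardless of attribution to the study treatment or procedure", but this is routine reporting of events not listed in Section 10.6.
- Section 10.62 concerns "late occurring AEs following completion of the Active Monitoring Phase", so it does not reach a patient still in observation.

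None of these removes the conflict.

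**5. What the optional count table could resolve.** The safety population is at most 128/2 = 64 per arm. The number still in observation at month 12 is not given, so 64, 58, 50 or 40 per arm is assumed. With no cases, the exact two-sided 95% upper limit is 1 - 0.025^(1/n), which gives 5.6%, 6.2%, 7.1% and 8.8%. These limits show precision only. They are not evidence of harm or of a defect.

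**The case against.** The best defence is that the ADR/AER cell points back to Section 10, and that Section 10.11 says expedited reports follow the timeframes in Section 10.4. A careful site would read Section 10 and keep reporting. The manufacturer must also be told of any serious event within 24 hours of first knowledge (under Section 10.4), again with no month-6 limit. This narrows the practical risk. It does not remove the conflict, because footnote 3 qualifies the very cell that points to Section 10.

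A reader might go further and infer that late cytopenia is lost to the trial, or that Section 16.34 is wrong to use worst grade. The documents do not support either:
- Section 10.6 asks for neutrophil and platelet grading at every evaluation, which can be read as reaching months 9-60.
- An Evaluation/Observation form is completed at each observation visit. Its fields are not shown, so whether it captures the counts cannot be decided.
- Myelodysplasia and leukemia have their own route through Section 10.53 and the new-primary entry in event monitoring.
- Worst grade by event type is a conventional summary, Section 16.34 adds attribution and a review of patterns, and the monitoring board sees safety data at least twice a year (Section 16.51).
- The six-month window for routine forms is about twice the 12 weeks in which Section 16.52 expects toxicity, so that limit is defensible.

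Nor does the stopping rule rest on neutropenia being reversible. It counts only non-hematologic events of grade 4 or higher.

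**Conclusion.** The contradiction between Section 18.1, footnote 3, and Section 10.4, footnote 1, stands on the text. It is worth correcting as a cheap improvement to safety reporting. Its reach is 54 of 60 months of active monitoring for attributable serious events. The number of reports at risk cannot be estimated, because the documents give no late event rate and site practice is unknown. The conclusion assumes that footnote 3 means what it says and that some sites work from the timetable.

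The absence of a planned table of late counts is a separate and lesser matter. Section 16.34 does not distinguish a cytopenia that recovered from one that persisted, so such a table would add information, but it is a suggestion. The primary endpoint, sample size and stopping rule are unaffected.

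**What to change.** **Required.** Reword footnote 3 so that the month-6 limit applies only to the routine Nadir/AE form. State that expedited reporting after month 6 follows Section 10.4, footnote 1, together with Sections 10.52 and 10.53. Section 10.11 wants expedited events entered through routine reporting as well, so say where a late one is recorded. The cost is one amended footnote and a few more late reports.

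**Optional.** Add to Section 16.34 a descriptive by-arm table of neutrophil, platelet and hemoglobin grades from the blood counts already scheduled after month 6. Restrict it to eligible treated patients still in observation and before new lymphoma therapy. Show numbers at risk, exits by arm and growth-factor use at each visit. Section 13.4 moves patients out of observation at progression or new therapy, possibly at different rates by arm, and Section 9.3 permits growth factors that can mask low counts, so the table describes and does not test. It needs no new visits or blood draws. If the observation form does not already hold the counts, the added entry is at most 3 labs x 8 visits x 128 patients = 3,072 values before dropout.

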2.32 Measure Tregs and tissue monocytes in on-study FL tumor tissue

- 2.33 Measure serum cytokines and vitamin D at on study and month 6.
- 2.34 Evaluate beta-2 microglobulin plus LDH score as a prognostic factor.
- 2.35 Measure ALC, AMC, and ALC/AMC ratio at on study and after treatment.
- 2.36 Compare quality of life as measured by the FACT-Lym between arms.

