13.0 Treatment/Follow-up Decision at Evaluation of Patient

13.1 Patients will be evaluated per the test schedule during cycle 1 of treatment.

13.2 After treatment, patients will be observed at 3, 6, 9, 12, 18, 24, 30, 36, 48, and 60 months from day 1 of treatment.

13.3 Criteria for removing patients from treatment and initiating observation.

13.3.1 Requested withdrawal or patient non-compliance.

13.4 Patients who have progressive or relapsed disease, receive subsequent treatment for lymphoma, refuse further observation, or fail to return for evaluation during observation will go to event monitoring.

13.5 At 5 years from day 1 of treatment, all patients still on observation will go to event monitoring every 12 months until 10 years from time of registration per Section 18.0.

13.6 A patient is deemed *ineligible* if after registration, it is determined that at the time of registration, the patient did not satisfy each and every eligibility criteria for study entry.

The patient may continue protocol treatment at the discretion of the physician as long as there are no safety concerns, and the patient was properly registered. The patient will continue treatment (if no safety concerns), observation, and event monitoring as specified for all patients (or will be taken off study, if applicable).

- If the patient received treatment, the patient will continue treatment (if no safety concerns), observation, and event monitoring as specified for all patients.
- If the patient never received treatment, On-study material and the End of Active Treatment/Cancel Notification Form must be submitted. No further data submission is necessary.

13.7 A patient is deemed a *major violation*, if protocol requirements regarding treatment in cycle 1 of the initial therapy are severely violated that evaluability for primary end point is questionable. The patient may continue protocol treatment at the discretion of the physician as long as there are no safety concerns, and the patient was properly registered. The patient will continue treatment (if no safety concerns), observation, and event monitoring as specified for all patients.

13.8 A patient is deemed a *cancel* if he/she is removed from the study for any reason before any study treatment is given. On-study material and the End of Active Treatment/Cancel Notification Form must be submitted. No further data submission is necessary.

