16.0 Statistical Considerations and Methodology

16.1 Overview: This is a randomized phase III study designed to compare the complete response rate at 6 months between Rituximab (Arm A) and Zevalin (Arm B) for treatment of asymptomatic follicular lymphoma.

16.11 Primary Endpoint: The primary endpoint of this study is the complete response rate at the 6-month disease assessment which will be compared between the two arms. A patient is considered to be a complete responder if the objective status at the 6-month disease assessment is a complete response. Any patient not meeting the definition of a complete response will be considered as a non-responder for the primary endpoint. A modified intent-to-treat approach will be employed for the primary analysis such that all randomized subjects meeting the eligibility criteria who do not cancel participation prior to treatment initiation and did not experience a major treatment violation (during the first cycle of treatment) will be included in the primary analysis. Sensitivity analysis will be conducted including all patients who did not cancel participation prior to

treatment initiation. The percentage of patients in each response category (e.g., CR, PR, STAB, Relapse/PD) will also be tabulated by arm.

16.2 Statistical Considerations:

16.21 Statistical Design:

Previous studies of treatment with four doses of single agent Rituximab in this patient population have shown CR rates of 6-33% (9 and 10). In addition, preliminary results of an additional study, the RESORT ECOG trial, show a CR rate of 15% in this same population (11). This study is designed to detect an improvement in complete response rate from 20% with Rituximab (Arm A) to 50% with Zevalin (Arm B). The proportion of patients who have a CR at 6 months will be evaluated and compared between the two treatment regimens using a two-sided $\alpha=0.05$ continuity corrected Cochran–Mantel–Haenszel (CMH) test with stratification factors as defined in Section 5.0.

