The primary goal of this trial is to compare the CR rate at 6 months between Rituximab and Zevalin. We will randomize 116 evaluable patients in a 1:1 ratio to Rituximab or Zevalin. This final analysis will take place after all patients have completed the disease assessment at 6 months. A sample size of 58 evaluable patients per arm (116 total evaluable) provides 90% power to detect an improvement in complete response rate from 20% to 50%, using a two-sided chi-square test at a significance level of 0.05. To ensure that 116 evaluable patients are randomized, we will enroll/randomize **128 total patients**.

The CR rate in each arm will be estimated by the number of evaluable patients who achieve a CR as the objective status on the disease assessment at 6 months divided by the total number of randomized evaluable patients in that arm. The CR rates will be compared between the two arms. If the CR rate is higher in the Zevalin arm, where the p-value is less than 0.05, this will be considered sufficient evidence that the Zevalin arm may be recommended for further testing in subsequent studies.

This study will use a dynamic allocation procedure to allocate an equal number of patients to each of the two treatment regimens.(30) This procedure will balance the marginal distributions of the stratification factors between these two treatment arms. The stratification factors that will be used are listed in Section 5.0.

This study will be based on a modified intent-to-treat approach including all randomized patients meeting the eligibility criteria who do not cancel participation prior to treatment initiation and did not experience a major treatment violation (during the first cycle of treatment) based on the randomized treatment assignment.

The study will be permitted to be published after all patients have undergone the 6-month disease assessment to establish the CR rate between each arm. This essentially fulfills the first goal of the study. See Section 16.3 for further analysis plans.

16.23 Other considerations: Adverse events, quality/duration of response, and patterns of treatment failure observed in this study, as well as scientific discoveries or changes in standard care will be taken into account in any decision to terminate the study.

16.24 Sample Size: This study is expected to accrue a maximum of 128 patients unless undue toxicity is encountered.

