General (FACT-G) with 27 items and a lymphoma-specific concerns scale with 15 items, each item measured on a 0-4 scale (0=not at all; 4=very much). The FACT-G is a general measure of quality of life of cancer patients containing four subscales: physical well-being, social/family well-being, emotional well-being, and functional well-being. It is widely used in cancer clinical trials and is reliable and valid for general research purposes (33) The additional items of the lymphoma-specific concerns scale were developed to capture items relevant to the QOL of lymphoma patients. The FACT-Lym has been shown in a cohort of non-Hodgkin's lymphoma patients to be easy to administer, reliable, valid, and sensitive to change.(34) The recall period for the FACT-Lym is 7 days. The FACT-Lym will be administered to all willing patients via a paper booklet in clinic at baseline and at 3, 6, 9, 12, 18, 24, 30, 36, 48, and 60 months while the patient remains in the active monitoring phase of the study (on treatment or in observation). The FACT-Lym will be scored according to the published scoring algorithm with the following scale scores computed at each time point: physical well-being (PWB, 7 items, score range 0-28), social/family well-being (SWB, 7 items, score range 0-28), emotional well-being (EWB, 6 items, score range 0-24), functional well-being (FWB, 7 items, score range 0-28), FACT-G total score (PWB+ SWB+ EWB+ FWB, score range 0-108), FACT-LymS score (lymphoma-specific concerns, 15 items, score range 0-60), FACT-Lym total score (FACT-G+ FACT-LymS, score range 0-168), and the Trial Outcome Index (PWB+ FWB+ FACT-LymS, score range 0-116). A clinically meaningful change is defined as 2-3 points in the PWB and FWB (35) 3-7 points in the FACT-G total (35) and 3-5 points in the FACT-LymS (36).

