The primary QOL analysis will be conducted at the time of the primary clinical analysis and will include the baseline, month 3 and month 6 QOL data. Additional analyses will be conducted after patients have been followed for 3 years and for 5 years. The primary analysis will compare the FACT-TOI between arms at the 3 month and the 6 month time points using analysis of covariance adjusting for the baseline FACT-TOI score. Mean FACT-TOI will be graphically presented by arm using a mean plot with standard deviation error bars including all available data with patients according to the randomized treatment assignment. Baseline characteristics will be compared between arms within the subject of patients who provide QOL data at one or more time points using t-tests for continuous variables and chi-squared tests for categorical variables. To assess for selection bias, baseline characteristics for patients who provide QOL data at one or more time points will be compared to patients who do not provide any QOL data using t-tests for continuous variables and chi-squared tests for categorical variables. Subsequent analysis will include comparison of FACT-TOI area-under-the-curve from baseline to 6 months between arms using analysis of covariance adjusting for the baseline FACT-TOI score. Responder-type analysis will also be performed in which the percentage of patients who report a 6-point worsening from baseline at either 3 or 6 months will be compared between arms using a chi-square test . The "responder" definition will be investigated using cumulative distribution curves. Lastly, a

linear mixed-effects model will be used to compare the FACT-TOI over time between arms with the post-baseline FACT-TOI score as the modeled outcome and predictors are baseline FACT-TOI, arm, time (treated as a continuous variable and measured at the planned month of assessment), and treatment-by-time interaction. Similar analyses described for the FACT-TOI will be repeated for the other scale scores, and for all scales after 3 and 5 years of follow-up.

Missing data will be handled in several ways. All analyses will first be completed using all available data, followed by analyses completed using imputed data using the arm minimum followed by the arm maximum. Lastly, we will employ pattern mixture models for longitudinal analyses. Output from all analyses will be compared to assess the degree to which missing data impacts study results.

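### Late FACT-Lym scores come only from patients still progression-free and untreated, so the 3- and 5-year between-arm QOL tests are not comparisons of the randomised arms

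*Combined protocol and SAP*

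**What the plan says.** Goal 2.36 is to "Compare quality of life as measured by the FACT-Lym between arms". Section 16.47 schedules the FACT-Lym at baseline and at ten visits from month 3 to month 60, "while the patient remains in the active monitoring phase of the study (on treatment or in observation").

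Section 13.4 defines who leaves that phase: "Patients who have progressive or relapsed disease, receive subsequent treatment for lymphoma", together with those who refuse further observation or do not return, go to event monitoring. The tables in Section 18.1 list the questionnaire booklet for active monitoring only. Event monitoring has a single 12-monthly form.

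The primary QOL analysis in 16.47 is an ANCOVA of FACT-TOI at months 3 and 6, adjusted for baseline. Area-under-the-curve, responder and mixed-model analyses follow. The analyses are then repeated for the other scales and "for all scales after 3 and 5 years of follow-up", with 0.05 as the significance level throughout. For missing data, 16.47 plans available-data analysis, imputation with the arm minimum and then the arm maximum, and pattern-mixture models.

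**The concern.** At month 36 or 60 a score exists only if the patient has neither progressed nor started new treatment. Section 1.3 hypothesises that more Zevalin patients will be progression-free at 3 and 5 years. The late test therefore conditions on a post-randomisation outcome that the trial expects to differ by arm, and the more strongly the hypothesis holds, the less the comparison is a randomised one.

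This matters because Section 1.2 names avoiding chemotherapy and preserving QOL among the key issues for these patients. A QOL gain from delaying progression or chemotherapy would mostly appear after the point at which collection stops. Nothing in 16.47 says that the late results describe progression-free patients, so a null result could be published as showing no QOL difference between the randomised arms.

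**Working it through.** **The plan's own figure.** The documents give no sample size for QOL. The trial's figure is 58 evaluable per arm for CR of 20% vs 50%, two-sided 0.05, 90% power.
- Without continuity correction: n0 = [1.960·√(2·0.35·0.65) + 1.282·√(0.2·0.8 + 0.5·0.5)]² / 0.30² = 51.0.
- With it: n = (n0/4)·[1 + √(1 + 4/(n0·0.30))]² = 57.5, so 58. Reproduced.

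**Inputs from the documents.** Section 1.2 gives 3-year PFS after single-course Zevalin of 63% in one study overall and 75% in its patients without GELF criteria.

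**Assumed inputs.** The documents do not give these:
- rituximab 3-year PFS 50–60%;
- FACT-TOI SD 15;
- a 10-point loss after progression;
- correlation ρ = 0 or 0.3 between underlying QOL and staying progression-free;
- correlation r = 0.5–0.7 between baseline and later score.

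Deaths are ignored (3-year OS in the same study was 90–97%).

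**Who still contributes at month 36, out of 58.**
- Zevalin: 58·0.75 ≈ 44, or 58·0.63 ≈ 37.
- Rituximab: 58·0.50 = 29, or 58·0.60 ≈ 35.
- These are upper limits, because next treatment, refusal and non-return also end collection.

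**What is lost.** With loss L after progression, the all-randomised difference is L·(pB − pA). Among progression-free patients with ρ = 0 it is 0.

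**What selection adds.** With a threshold on a normal variable, the mean latent score among those retained is ρ·m(p), where m(p) = φ(z)/p and z = Φ⁻¹(1−p). This gives m = 0.424 (75%), 0.599 (63%), 0.644 (60%) and 0.798 (50%).
- The raw difference among progression-free patients is 15·ρ·[m(pB) − m(pA)]. For 75% vs 50% and ρ = 0.3 it is 4.5·(0.424 − 0.798) = −1.7.
- The plan specifies ANCOVA on baseline, not a raw difference. If selection acts through the current score, the adjusted difference is about raw·(1 − r²).
- If selection acts through the measured baseline score, the adjusted difference is about 0.

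| PFS Zevalin / rituximab | True difference | Shown, ρ = 0 | Raw, ρ = 0.3 | ANCOVA, ρ = 0.3 through current QOL (r = 0.7 to 0.5) |
|---|---|---|---|---|
| 75 / 50 | +2.5 | 0 | −1.7 | −0.9 to −1.3 |
| 75 / 60 | +1.5 | 0 | −1.0 | −0.5 to −0.7 |
| 63 / 50 | +1.3 | 0 | −0.9 | −0.5 to −0.7 |
| 63 / 60 | +0.3 | 0 | −0.2 | −0.1 to −0.2 |

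A simulation with one million patients per arm reproduced the ANCOVA columns to within 0.05 points.

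**Mixed model.** It also uses earlier scores from patients who later progress. Simulated with PFS 75% vs an assumed 45–55%, it gave about +1.2 to +2.2 with full data. With scores stopping before progression it gave −0.4 to +0.5 (simulation error about 0.35). If the visit that detects progression still yields a booklet, it gave about +0.7 to +1.3: attenuated, not abolished.

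**Planned safeguards.** In the same 75% vs 45–55% scenarios, arm-minimum imputation gave about +4 to +8 points and arm-maximum about −6 to −10. They bracket zero widely and do not locate the effect. The pattern-mixture models have no stated identifying restrictions and no score after event monitoring starts. The selection-bias check compares patients with any QOL data against those with none, so a patient who stops at progression counts as having data.

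**The case against.** The strongest reply is that QOL is a correlative goal whose declared primary analysis is at months 3 and 6. By the schedule in Section 4.0 the first post-treatment imaging is at month 6, and the booklet is completed before response is discussed, so few of those scores are lost. This stands.

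The sizes are also modest and rest on assumptions. A 2.5-point difference on an assumed SD of 15 is 0.17 SD, below the 0.20 that 16.47 calls trivial. With 44 vs 29 patients the ANCOVA standard error is 15·√(1−r²)·√(1/44+1/29) = 2.6 to 3.1 points, larger than the bias. No passage shows that radiological progression in asymptomatic patients lowers FACT-TOI by 10 points. The only rituximab-induction figure at 3 years (78% free of retreatment, Section 1.2) is a different endpoint. With equal PFS there is no bias. All of this limits the size; it does not change what the comparison measures.

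A reader might infer that the late result will point the wrong way by as much as 1.7 points. The documents do not support that: 1.7 is a raw mean difference, whereas 16.47 adjusts for baseline. A reader might also infer that every QOL benefit of delayed progression is removed. That is too strong, because the mixed model keeps earlier scores from later progressors and the visit that detects progression may yield a last booklet.

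Finally, the missing-data analyses would show that results are sensitive. They would, but they cannot recover the missing effect or tell the reader that progression is the cause.

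**Conclusion.** The point holds as a matter of what the late comparison means. Sections 13.4, 16.47 and 18.1 together restrict scores at months 36, 48 and 60 essentially to patients still progression-free and untreated, while 16.47 tests them between arms as if they represented all randomised patients.

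Bias toward no difference needs two conditions: PFS differs by arm, and QOL is lower after progression. With SD 15, a 10-point loss and 3-year PFS of 75% vs 50–60% or 63% vs 50%, a true benefit of 1.3 to 2.5 points appears as about 0; at 63% vs 60% only 0.3 points are at stake. A reversal of about −0.5 to −1.3 points after baseline adjustment needs a third condition, selection through current QOL that the baseline score does not capture. The direction of the bias follows from the design; its size depends on assumed figures. The month 3 and 6 inference and the primary and secondary endpoints do not depend on it.

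**What to change.** Amend Section 16.47 so that:
- QOL after month 6 is reported as *QOL while progression-free and untreated*;
- the number of patients contributing is shown per arm and time point;
- no between-arm p-value or significance claim is attached to those later results;
- months 3 and 6 remain the between-arm QOL inference.

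This is a wording change with no new data collection. Its cost is a narrower late QOL claim.

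Giving the booklet during event monitoring as well would allow a comparison of all randomised patients, but it is optional. Event monitoring is a 12-monthly form rather than a clinic visit, 16.47 specifies completion in clinic, and 3.19f asks patients to return only during active monitoring. Booklets would probably have to be mailed, with a change in mode of administration and lower completion.
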